acid (UDCA) could enhance the bile synthesis by CYP7A1 altering the gut microbiota population. UDCA also has other beneficial effects, such as anticholestatic, antifibrotic, antiproliferative, and anti-inflammatory [12-14].

In retrospective studies, statins appear to be safe in patients with compensated cirrhosis, and evidence suggests that they may significantly reduce fibrosis (HR:0.56, p<0.0001)[15]. Preclinical data from studies performed on in vitro and in vivo animal models shed light on favorable effects of statins on endothelial function, angiogenesis, PHTN, and fibrosis. Suggested mechanisms involve regulation of KLF2, eNOS, thrombomodulin, and C-natriuretic peptide. Animal studies evidence suggests that the administration of fluvastatin, lovastatin, and simvastatin to primary rat hepatocytes and human hepatoma cell line inhibits the paracrine activation of HSCs [16], reduces HSC turnover and activity [17,18]. Moreover, Nature (2020) reported statin therapy is associated with lower prevalence of gut microbiota dysbiosis. [19]

The combination of ursodeoxycholic acid and statins is safe in human experiments, and the combination of the two has also proved to have a synergistic effect on the reduction of bile cholesterol levels [20], but there is no research on improving fibrosis makers or improving intestinal flora.

The goal of the current study was to evaluate our hypothesis model of pathogenesis of chronic inflammation of liver cirrhosis. We hypothesized that an adverse microbiome would exacerbate the histopathological severity of liver induced by CCL4 in a germ-free mice model. We transplanted these mice with human fecal samples from healthy controls, or liver cirrhosis treated with statin, or UDCA. The clinical trial mainly explores whether single statin or combined ursodeoxycholic acid can reduce liver fibrosis indicators, inflammatory cytokines and intestinal flora imbalance in patients with liver cirrhosis who have been cured of chronic hepatitis C or non-viral load hepatitis B.

Patients and assessments- Study design

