We expect to enroll 120 stable patients who have achieved sustained viral response (SVR) (ie, viral eradication) after hepatitis C treatment for 6 months, or non-viral load hepatitis B for 6 months, who have been diagnosed with primary cirrhosis (FIB-4 \geq 3.25) and met the Baveno VII criteria (liver stiffness measurement [LSM] \geq 25 kPa) and exclude it (LSM <15 kPa and platelet count [PLT] \geq 150 \times 10⁹/L) were used. Grey zones were classified into two groups: (high – LSM between 20–25 kPa and PLT <150 \times 10⁹/L, or LSM between 15–20 kPa and PLT <110 \times 10⁹/L, or low – defined as the remaining patients within the grey zone) [27]. **Exclusion conditions:** already taking statins, diabetes, liver cancer, alcoholic liver, moderate to severe fatty liver, liver decompensation (jaundice, ascites, esophagogastric varices, history of hepatic coma), chronic kidney disease, antibiotic use within three months and gastric ulcer medication(such as PPIs). Randomly divided into three groups: **Group 1:** control group (n =

30), Group 2: treatment group (ursodeoxy Cholic acid (UDCA) (10mg/kg/day) (n = 30), Group 3: treatment group (simvastatin 40mg) (n = 30), Group 4: treatment group (simvastatin 40mg/day + ursodeoxy Cholic acid (UDCA) (10mg/kg/day) (n = 30). Fecal bile acid content and fecal flora, skin bile acid profile, cytokine markers, biochemical fibrosis biomarker were collected at the test base point and six months after treatment. In addition, patients who achieved virus eradication without liver cirrhosis (FIB-4 < 1.45, n=30) collected the content of fecal bile acid, fecal flora, skin bile acid, and inflammatory cytokines were collected at the test base point index, biochemical fibrosis biomarkers. Analysis of flora: 16S ribosomal RNA gene sequence analysis from the patient's fecal tube. Analysis of total fecal bile acid: LC-MS/MS system analysis. Skin bile acid profile:Desorption-Electrospray Ionization Mass Spectrometry (TD-ESI/MS).

Block randomization

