Patients (n=120) were distributed on one block with 8 numbers and each group contained two numbers (1, 2, 3, 4). The admitted patients who were eligible for inclusion were given numbers in the order; number 1 was allocated to (control group) as the study group, patients who carried number 2 was allocated to (UDCA group),patients who carried number 3 was allocated to (simvastatin group), and number 4 was allocated to (simvastatin plus UDCA group). Therefore, the control and three interventional groups were randomized into 1:1:1:1.

Stool sample preparation and microbiota analysis

Bile juice and biliary stents samples will be collected in separate sterile containers containing 2mL of RNA later and will be stored at room temperature. The samples will be transferred to the laboratory within 12 h, stored at 4°C, and used for extracting DNA within few weeks. Preliminary experiments will confirm that the bacterial composition data does not change in four weeks under the storage conditions used. Genomic DNA will be isolated from stool samples using the CTAB/SDS methods (Novogene Laboratories) following the manufacturer's protocol. All microbial community DNA samples will be analyzed for V4 variable region of bacterial 16S ribosomal RNA gene using PCR primers 515F and 806R. The PCR products will be separated by 2% agarose gel electrophoresis. Samples with bright main strip between 400-450bp will be chosen for further experiments. PCR product will be mixed in equidensity ratios. Then, mixture PCR products will be purified with Qiagen Gel Extraction Kit (Qiagen, Germany). Sequencing libraries will be generated using TruSeq DNA PCR-Free sample Preparation Kit (Illumina, USA) following manufacturer's recommendations and index codes will be added. The library quality will be assessed on the Qubit® 2.0 Fluorometer (Thermo Scientific) and Agilent Bioanalyzer 2100 system. At last, the library will be sequenced on an IlluminaHiSeq2500 platform and 250 bp paired-end reads will be generated.

Fecal bile acid profile [20].

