TD-ESI source comprised of a direct probe (DP), thermal desorption unit, and electrospray ionization device. First, the direct probe (DP) was used for sampling analytes in solution or on solid surfaces. For liquid samples, a stainless steel inoculating loop serving as a probe (2 mm in diameter) was used to obtain approximately 2 μ L of sample solution for each analysis. For viscous solutions or solid samples, a straight fine needle (350 μ m in diameter) was used to either collect analytes of viscous solutions or sweep five times across solid surfaces to obtain analytes. Second, the function of the thermal desorption unit was to vaporize samples on the DP and introduce desorbed analytes into the ESI plume through a quartz tube with single taper (OD= 6 mm, ID= 4 mm, Length= 80 mm) so that effective sample ionization can take place. In addition, an opening in the thermal desorption unit was created when the direct probe was removed from the unit to sample analytes. The thermal desorption unit was sealed after the direct probe was placed back on the thermal desorption unit for analysis of sample analytes on the probe. Third, an electrospray ionization device was used for post-ionizing desorbed analytes. The high voltage and solvent flow rate required to generate an electrospray plume were 5 kV and 2.5 μ L/min, respectively. The ESI solution was a methanol and water mixture (1:1, v/v) containing 0.1% acetic acid, and was delivered through a fused-silica spray capillary (ID= 100 μ m, OD= 375 μ m, Polymicro, Phoenix, AZ) into the mass inlet of the mass spectrometer. The TD-ESI source was attached to a triple quadruple mass spectrometer (Agilent 6410) to detect the analyte ions. To obtain a stable solvent and analyte ion signal, the electrospray capillary was aligned to the MS inlet and the distance from the exit of the TD tube to the electrospray capillary (d_1) was kept at 8 mm, while the distance from the MS inlet to the electrospray capillary (d_2) was 5 mm. The temperature in the thermal desorption unit was set at 250 °C and was measured by a thermistor installed in the source. The flow rate of the nitrogen gas used to deliver desorbed analytes into the ESI plume was 0.8 L/min.

Primary end point: Fibrosis biomarker [23]

Molecular markers of fibrogenesis including TGF- β 1, and Type IV collagen. Hyaluronic Acid in the serum blood test, and clinical laboratory FIB-4 Index.

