Secondary end points: 1. Cirrhosis dysbiosis ratio (CDR), the ratio of autochthonous good bacteria (e.g. Lachnospiraceae, Ruminococcaceae and Clostridiales) to non-autochthonous/ pathogenic bacteria (e.g. Enterobacteriaceae and Streptococcaceae). 2. Total stool bile acid, Secondary and primary bile acid ratio. 3. Serum inflammation peptides (IL-6, IL-8, IL-10, and TNF-a)

Sample size : Till now, there was no prospective data to support the evaluation the sample size of study in the liver fibrosis deminition after the administrations of stain and UDCA. Prior data [24]may indicate the effect of 40 mg simvastatin versus placebo on hepatic portal pressure was studied over a period of 3 months. A significant decrease in HVPG (-15%) was noted in the experimental group versus no change in the placebo group. The study included 24 cases in each study arm. Therefore, we plan to enroll 30 participants in each arm.

Safety

Initial dose of study drug is 20 mg which can be increased to 40 mg after 4 weeks if the participant does not develop side effects. Creatine kinase and standard biochemistry including liver enzymes are measured for safety reasons after 2 weeks, to rule out myositis and liver damage. Side effects and events are consecutively registered throughout the trial. Safety of statins in chronic liver disease has been assessed in only a few clinical trials, but reviews of observational studies report high safety and low risk of adverse events, even significantly lower the all-cause mortality [25,26]

Statistical analysis:

Risks are reported as IRRs along with their 95% confidence intervals and P values. For subgroup analyses according to sample characteristics, P values for interaction also are assessed. The cumulative proportion of patients developing liver fibrosis events during follow-up is estimated by life table methods and log-rank tests were reported. P values are 2-sided, and values of .05 or less are considered statistically significant. All statistical analyses are performed using SAS version 9.1 (SAS Institute Inc).

Limitation 1:

If post treated human feces contain the trace level of drug, the hypothesis that it is caused by microorganisms alone does not hold. We will check the post treated human feces by the TD-ESI (LTQ)for simvastatin (Formula: $C_{25}H_{38}O_5$, Exact mass: 418.57 Da),and Ursodeoxycholic acid (UDCA)(Formula : $C_{24}H_{40}O_4$. Exact mass : 392.29 Da). The pre-test was performed by TD-ESI (LTQ) as followed figures.

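### The 30 per arm does not follow from the portal-pressure study it rests on, and the stated analyses estimate neither the drug effects on the fibrosis markers nor their interaction

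*Protocol*

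**What the plan says.** **Sizing.** The Sample size paragraph of the protocol opens by acknowledging that no prospective data exist for sizing a fibrosis outcome under these drugs. It then turns to a 3-month comparison of simvastatin 40 mg with placebo on portal pressure, with 24 per arm: "A significant decrease in HVPG (-15%) was noted in the experimental group versus no change in the placebo group". It concludes: "Therefore, we plan to enroll 30 participants in each arm". It gives no target effect on any marker, no SD, no power and no dropout rate.

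**Endpoint.** The primary endpoint section begins "Molecular markers of fibrogenesis including TGF" and lists TGF-beta1, type IV collagen, hyaluronic acid and FIB-4. Under Study design, samples are taken at baseline and six months. Portal pressure (HVPG) is neither an endpoint nor a listed measurement.

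**Layout.** Study design lists control, UDCA, simvastatin and both ("Group 4: treatment group (simvastatin 40mg/day + ursodeoxy Cholic acid (UDCA) (10mg/kg/day) (n = 30"), and says "We expect to enroll 120 stable patients". Block randomization confirms that "the control and three interventional groups were randomized into 1:1:1:1".

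**Analysis.** The Statistical analysis paragraph names incidence rate ratios (IRRs) with confidence intervals, life tables and log-rank tests for fibrosis events, and interaction P values for subgroups defined by sample characteristics. It names no comparison of marker values between arms, no marginal drug effect and no simvastatin-by-UDCA interaction.

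**The concern.** There are two linked problems.

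First, the number of patients is presented as a consequence of a study that cannot support it. The outcome differs (portal pressure against serum markers and FIB-4), as does the time point (three months against six). The comparison also differs: one simvastatin-placebo contrast against four arms, two of which contain UDCA. A significant result on HVPG with 24 per arm says nothing about what 30 per arm can show on these markers. Because the protocol does not state what effect it can detect, a null result on a marker could be taken as evidence of no effect when only a large one could have been found.

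Second, the methods the protocol does fix do not fit its primary endpoint. IRRs and log-rank tests analyse events over time. The primary markers are values measured at baseline and at six months. Nothing stated turns those values into an estimate of what simvastatin does, what UDCA does, or whether the two together differ from the sum of their separate effects. The 1:1:1:1 layout allows all three to be estimated from data the trial already collects.

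**Working it through.** **1. Can 30 be reproduced?** The stated inputs are 24 per arm in the source study, HVPG -15% against no change, and two-sided 5%. No SD, power or dropout rate is stated. Two routes reach 30, but only by adding an unstated number:
- 24 / (1 - 0.20) = 30, with an assumed 20% dropout.
- n = 2 x (1.96 + 0.84)² x (SD / 15)² = 30 per arm, with an assumed SD of about 20.7 percentage points and 80% power.

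Both are fitted backwards, and both would size an HVPG comparison. Neither counts as a derivation for this trial.

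**2. Source study and this trial side by side**

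| | Source study | This trial |
|---|---|---|
| Outcome | HVPG | TGF-beta1, type IV collagen, hyaluronic acid, FIB-4 |
| Time point | 3 months | 6 months |
| Arms | simvastatin, placebo | control, UDCA, simvastatin, both |
| Per arm | 24 | 30 |

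**3. What the planned numbers can detect.** From the protocol: 30 per arm, four arms, two-sided 5%. Assumed: a continuous marker expressed in SD units (no SD is given), 80% power, no baseline adjustment.

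Standard errors in SD units:
- One arm v control: sqrt(2/30) = 0.258
- Margin, 60 v 60: sqrt(2/60) = 0.183
- Interaction (a difference of differences over four arms): sqrt(4/30) = 0.365

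The normal approximation to the detectable effect is (1.96 + 0.84) x SE:
- Pairwise: 2.80 x 0.258 = 0.72
- Margin: 2.80 x 0.183 = 0.51
- Interaction: 2.80 x 0.365 = 1.02

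In the table, the pairwise and margin figures use the t distribution and are slightly larger; the interaction uses the approximation. The Bonferroni column uses 0.05/4 = 0.0125. An assumed 20% loss leaves 24 per arm and 48 per margin, and the interaction becomes 2.80 x sqrt(4/24) = 1.14.

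| Contrast | One marker | Bonferroni, four markers | One marker, 20% loss | Bonferroni, 20% loss |
|---|---|---|---|---|
| Arm v control | 0.74 | 0.89 | 0.83 | 1.00 |
| Margin | 0.52 | 0.62 | 0.58 | 0.69 |
| Interaction | about 1.0 | - | about 1.1 | - |

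Power for a true effect of 0.5 SD on one marker, with no loss, is 48% for 30 v 30 and 78% for 60 v 60.

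**4. Baseline adjustment.** Adjustment multiplies each detectable effect by sqrt(1 - r²). For an assumed baseline to six-month correlation of r = 0.5 the factor is 0.866; for r = 0.7 it is 0.714. Every figure above falls by 13% to 29%, for pairwise, margin and interaction alike. For example, 0.74 becomes 0.64 to 0.53, and 0.52 becomes 0.45 to 0.37.

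**5. When a margin answers the single-drug question.** The simvastatin margin is the average of its effect without UDCA and its effect on top of UDCA. If those were 0 and 0.8 SD, the margin would be (0 + 0.8)/2 = 0.4 SD, which is true of neither setting. The interaction would be 0.8 SD, below the 1.0 SD that the trial can detect. The smaller standard error of the margin is real, but it applies to the single-drug effect only without material interaction.

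**The case against.** The strongest defence is that the protocol is candid. It says that fibrosis data are lacking, introduces the HVPG study as something that may be indicative, and claims no power. That stands. A reader might infer that the trial misses a power target or advertises itself as adequately sized; the text supports neither.

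A reader might also infer that the plan judges each drug on 30 v 30 and discards half its information. The protocol does not say so: it names no between-arm contrast, and a statistical analysis plan that is not at hand may supply one. The choice between margins and arm contrasts can properly be left there. What can be said is that the methods the protocol does fix do not address marker values.

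Nor should the margins simply become the main analysis. The stated aim asks about a statin alone or combined with UDCA, which is a question about arms, and the trial cannot reliably check the no-interaction condition.

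Finally, one might read a synergy hypothesis into the protocol, since the introduction says that "the combination of the two has also proved to have a synergistic effect on the reduction of bile cholesterol levels". That concerns bile cholesterol, which is not an endpoint here, and the same sentence says there is no research on fibrosis markers. The interaction is worth estimating because the layout contains a combination arm, not because the protocol promises synergy on fibrosis.

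**Conclusion.** The point holds in two limited parts. The step from the HVPG study to 30 per arm is unsupported, and the detectable effect is not stated. The analyses the protocol names do not estimate the drug effects on its primary markers or their interaction, although the four equal arms allow both.

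Without baseline adjustment, a single arm-v-control comparison has 80% power only for differences of 0.74 to 1.00 SD, depending on multiplicity adjustment and on an assumed loss of 0 to 20%. The margins detect 0.52 to 0.69 SD over the same range. The interaction, at about 1.0 to 1.1 SD without multiplicity adjustment, can be estimated but not usefully tested.

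These figures are in SD units because the protocol gives no marker SD. The loss rate and the baseline correlation are assumptions. Nothing here shows that 30 per arm is the wrong number or that N should change.

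**What to change.** Leave N unchanged and make two changes before outcome data are seen.

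1. **Analysis.** For each primary marker, fit one model of the six-month value adjusted for its baseline value, with simvastatin (yes/no), UDCA (yes/no) and their interaction. Report the arm-v-control effects, the interaction with its 95% CI and the two 60 v 60 margins side by side. State that a margin is read as the single-drug effect only if there is no material interaction.

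2. **Sample size text.** Remove the inference from the HVPG study. Say that 30 per arm is pragmatic, and give the detectable effects from the table above: with and without adjustment for four markers, with and without the assumed loss, and for pairwise, margin and interaction contrasts alike. Note the 13% to 29% reduction under the assumed baseline correlations, and say that the interaction will be estimated with its interval and that a non-significant test will not be taken as evidence of no interaction.

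**Cost.** A little more analysis and some rewording, with no added patients, visits or measurements. The stated detectable effect will look less favourable than the present text suggests, and the margins average over the other drug, so they must not be shown without the interaction beside them.

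### Read from treatment start, the one stated laboratory safety check (week 2) precedes the possible step to 40 mg (week 4), so its stated purpose is not met at the dose that defines Groups 3 and 4

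*Protocol*

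**What the plan says.** The protocol's study design section fixes both simvastatin arms at 40 mg and mentions no titration: "Group 3: treatment group (simvastatin 40mg) (n = 30") and "Group 4: treatment group (simvastatin 40mg/day + ursodeoxy Cholic acid (UDCA"), also with 30 participants.

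The Safety section describes a titration: "Initial dose of study drug is 20 mg which can be increased to 40 mg after 4 weeks", on the condition "if the participant does not develop side effects". The next sentence gives the laboratory check and its purpose: "Creatine kinase and standard biochemistry including liver enzymes are measured for safety reasons after 2 weeks, to rule out myositis and liver damage". That sentence does not say from when the two weeks run. The section then has side effects and events recorded throughout the trial.

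No other creatine kinase measurement is stated. The remaining sampling, at baseline and six months, is for end points. The primary end point section lists TGF-β1, type IV collagen, hyaluronic acid and FIB-4.

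**The concern.** The check has a stated job, to exclude muscle and liver injury, and the arms it protects are defined by 40 mg. If it takes place before anyone can have reached 40 mg, a normal result speaks only to 20 mg. A site that follows the written schedule would then complete the check and still have no creatine kinase value from the dose under study, with or without UDCA.

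The second difficulty is the link between the check and the increase. The condition for the increase refers to side effects, a term the protocol does not define. Nothing says whether an abnormal laboratory value without symptoms counts as one, so sites could apply the condition differently.

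The participants have cirrhosis. The Safety section itself notes that few clinical trials have examined statin safety in chronic liver disease, although it adds that reviews of observational studies are reassuring. Laboratory data at 40 mg are what the trial would need for a safety statement about that dose.

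**Working it through.** No sample-size or error-rate figure is involved. The check sets the stated times against the stated doses.

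**Inputs from the protocol**
- Safety: start at 20 mg, earliest increase to 40 mg at week 4, laboratory check at two weeks.
- Study design: Groups 3 and 4 at 40 mg, 30 participants each, final sampling at six months.

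**Assumptions**
- The study drug in the Safety section is simvastatin, because the 40 mg matches Groups 3 and 4 (UDCA is dosed per kilogram).
- Treatment runs to the six-month sampling, since no other duration is given. Six months is taken as 26 weeks.

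**Where the check falls under each reading**

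| Reading | Week of check | Dose at check |
|---|---|---|
| Two weeks from treatment start, with titration | 2 | 20 mg |
| Two weeks from the increase at week 4 | 4 + 2 = 6 | 40 mg |
| Two weeks from start, no titration (design section taken alone) | 2 | 40 mg |

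The first row is the plain reading. The neighbouring four-week interval runs from the initial dose, and no other starting point is given for the two weeks. Under it, the check comes 4 − 2 = 2 weeks before the earliest possible increase, so everyone tested is on 20 mg.

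**Size under the first reading**
- Time on 40 mg with no stated creatine kinase measurement: at most 26 − 4 = 22 weeks.
- Share of treatment: 22 / 26 = 0.846, about 85%.
- Participants affected: at most 30 + 30 = 60. Both figures are upper limits, because the increase is optional and may come later than week 4.

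**What else is measured on 40 mg**
- Creatine kinase: nothing stated.
- Liver enzymes: FIB-4 at six months implies aminotransferase values. The protocol does not print the formula, so this relies on the usual definition of the index. These values come at the end of treatment and serve an end point.
- Clinical events: recorded throughout, with no laboratory test attached.

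**Link to the increase**

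The condition names side effects only. The laboratory sentence names a purpose but no consequence. Neither sentence refers to the other.

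**The case against.** The strongest reply is that the two weeks have no anchor. The sentence follows directly on the one about the increase, so it could mean two weeks after that step. The check would then fall at about week 6, on 40 mg, and the ordering problem would disappear. This stands as a possibility, and it limits the finding to the plain reading. It does not remove the defect, because a safety time point that can be read as week 2 or week 6 needs to be fixed in the text.

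A second reply is that the problem belongs to the mismatch between the titration and the fixed 40 mg arms. If the design section were taken alone, the check would fall on 40 mg. That is right: the ordering problem depends on the titration, and one reconciliation should settle both. Writing the titration into the arm definitions would, however, leave the ordering problem in place.

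Two stronger readings are tempting, and the documents do not support them:
- **No laboratory evidence of liver injury on 40 mg.** A reader might infer this, but the six-month FIB-4 implies some enzyme values in all four arms. The gap is mainly in creatine kinase, and in enzyme values designated for safety.
- **The protocol permits the increase despite an abnormal two-week result.** A reader might infer this by taking side effects to mean symptoms only. The term is undefined, and a test at week 2 can equally be read as informing a decision at week 4. The text is silent on the link; it does not grant permission.

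Ongoing recording of side effects is real surveillance, but it would not by itself show a laboratory change without symptoms.

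**Conclusion.** The point holds on the plain reading. Counted from treatment start, the one stated laboratory safety check falls wholly within the 20 mg period, so its stated purpose is not met at the dose that defines Groups 3 and 4. No later creatine kinase measurement is stated for up to 22 of 26 weeks in up to 60 participants. Whether the two-week result bears on the increase is also left open.

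This rests on three things: treatment start as the anchor, the 20-to-40 mg titration being intended, and six months taken as 26 weeks of treatment. If the two weeks run from the increase, or if there is no titration, the check falls on 40 mg; the missing anchor and the unstated link to the increase would remain.

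A reader might want an expected number of missed laboratory abnormalities. The documents give no rate for such events, so any figure would only restate an assumed one, and none is offered here. The primary end point is not affected. The matter is whether the protocol's own safety check does what it says.

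**What to change.** Reconcile the Safety sentences with each other and with the 40 mg arm definitions in the study design section, so that the text:

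1. states from when the two weeks are counted;
2. makes the laboratory check serve its stated purpose for the dose that defines Groups 3 and 4;
3. says whether the result of the check bears on the increase, and whether side effects include laboratory abnormalities.

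The clinical team sets the times and limits; no schedule or threshold is proposed here. On the reporting side, tabulate laboratory safety results by arm and by the dose being taken when the sample was drawn, so that values on 20 mg are not read as evidence about 40 mg.

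The cost is a few sentences of protocol text, with a small laboratory cost if the reconciled schedule includes a further check.

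### The life-table and log-rank analysis of liver fibrosis events matches no listed endpoint: the event is undefined, and all 11 endpoint quantities are measured values or ratios collected at baseline and six months

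*Protocol*

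**What the plan says.** The Statistical analysis section of the protocol reports risks as IRRs with 95% confidence intervals, provides for interaction P values in subgroups, and sets two-sided significance at 0.05. On the fibrosis outcome it says: "The cumulative proportion of patients developing liver fibrosis events during follow-up is estimated by life table methods and log-rank tests were reported". The phrase for the event occurs only there.

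The endpoints are listed separately:

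- **Primary:** TGF-beta1 and type IV collagen, followed by "Hyaluronic Acid in the serum blood test, and clinical laboratory FIB-4 Index".
- **Secondary:** the cirrhosis dysbiosis ratio (CDR); "Total stool bile acid, Secondary and primary bile acid ratio"; and "Serum inflammation peptides (IL-6, IL-8, IL-10, and TNF-a").

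On timing, the Study design section lists the fecal and skin measurements and then "cytokine markers, biochemical fibrosis biomarker were collected at the test base point and six months after treatment". On population, the same section enrols patients "who have been diagnosed with primary cirrhosis (FIB-4" of at least 3.25). On the aim, the end of the introduction asks whether treatment "can reduce liver fibrosis indicators, inflammatory cytokines and intestinal flora imbalance".

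**The concern.** A life table and a log-rank test need an event, a time at which it occurs, and a schedule that can detect it. The protocol supplies none of these for fibrosis. What it supplies is a set of laboratory quantities measured before and after treatment.

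This is not a detail that a statistical analysis plan would normally fill in. The protocol does state a method, and that method does not fit its endpoints. Two things are at stake:

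- Followed literally, the sentence gives no estimate of the effect of simvastatin, UDCA or the combination on any endpoint.
- To carry it out, someone must create an event, and a cut-point if a marker is used. Nothing in the protocol prevents that from happening after the data are seen.

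**Working it through.** **1. Is any endpoint an event?**

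| Endpoint group | Quantities | Count | Events |
|---|---|---|---|
| Primary | TGF-beta1, type IV collagen, hyaluronic acid, FIB-4 | 4 | 0 |
| Secondary 1 | CDR | 1 | 0 |
| Secondary 2 | total stool bile acid, secondary/primary bile acid ratio | 2 | 0 |
| Secondary 3 | IL-6, IL-8, IL-10, TNF-a | 4 | 0 |
| Total | | 4 + 1 + 2 + 4 = 11 | 0 |

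This is the only count that comes from the document itself. Everything from step 4 on rests on assumed inputs.

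**2. Could the event be new fibrosis?** No. Randomised patients already have cirrhosis at entry.

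**3. Could it be a marker crossing a threshold?** FIB-4 cut-offs do appear (at least 3.25, below 1.45), but only to define entry and the non-cirrhotic comparison group. With samples at baseline and six months, any event of this kind would be found at one common time. With a and b events in arms of n each, N = 2n and D = a + b, the log-rank statistic at a single time is

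(a − D/2)² / [D × ¼ × (N − D)/(N − 1)],

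which equals the Pearson chi-square times (N − 1)/N.

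Assumed example, 12/30 against 6/30:

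- Log-rank: D = 18; variance = 18 × 0.25 × 42/59 = 3.203; (12 − 9)²/3.203 = 2.810.
- Pearson: 0.2²/(0.3 × 0.7 × 2/30) = 2.857, and 2.857 × 59/60 = 2.810.

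The two agree. The test is then a comparison of two proportions and carries no information about time.

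**4. Illustration: the cost of cutting a marker into an event.** The protocol gives no SD, target effect or power. Assume a normal marker, 30 against 30, two-sided 0.05 and no dropout. The difference with 80% power as a continuous outcome (noncentral t, 58 df) is 0.736 SD. Exact enumeration of the single-time log-rank test at that effect gives:

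| Cut-point | Control vs treated proportion | Power |
|---|---|---|
| Midpoint between the group means | 0.643 vs 0.357 | 0.622 |
| Control median | 0.500 vs 0.231 | 0.584 |
| Control 75th percentile | 0.250 vs 0.079 | 0.445 |
| Control 90th percentile | 0.100 vs 0.022 | 0.208 |

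**5. Illustration: a clinical event instead.** Take 30 against 30 with all events in controls at distinct times.

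- 3 vs 0: expected = 30/60 + 29/59 + 28/58 = 1.474; variance 0.750; chi-square = (3 − 1.474)²/0.750 = 3.11; p = 0.078.
- 4 vs 0: expected 1.948; variance 0.999; chi-square = (4 − 1.948)²/0.999 = 4.22; p = 0.040.

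So at least 4 of 30 controls (13%) need an event within six months even if treatment prevents every one. The binomial chance of at least 4 in 30 is 0.061, 0.353 or 0.678 at assumed control risks of 5%, 10% or 15%. The protocol gives no event rate.

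**The case against.** The best defence is that dated events could exist. The Safety section registers side effects and events throughout the trial, and patients with decompensation are excluded at entry, so a new liver event would be observable. A statistical analysis plan could define one. This stands to a point: the defect is a missing definition and missing endpoint status, not proof that no event could ever be analysed. It does not rescue the sentence. The protocol does not call those registrations fibrosis events or make them an endpoint, and a log-rank test on them would still address none of the 11 listed quantities.

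Nor does the protocol label the log-rank test as its primary analysis, so the text does not show that the markers would go unanalysed. It shows that the stated analysis names no comparison suited to them.

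Two stronger readings should be resisted:

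- A reader might infer a conflict of direction, because the aim is to reduce fibrosis indicators and the sample-size text refers to a "study in the liver fibrosis deminition after the administrations of stain and UDCA", while the analysis counts patients who develop events. There is no conflict. A trial that hopes to reduce fibrosis may coherently count adverse fibrosis outcomes and look for fewer of them.
- A reader might infer that the IRRs belong to the adverse events. The protocol does not say so. The IRR sentence stands in the same paragraph and is just as unattached to any listed endpoint.

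The power figures can also be challenged. They cover one pairwise comparison. If the arms were pooled as a factorial, 60 against 60 (a contrast the protocol does not state), the same effect and cut-points would give 90%, 87%, 73% and 44%. That objection is fair, and the finding does not depend on those figures. Finally, ANCOVA is not the only method that would fit; change scores or rank methods could also serve.

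**Conclusion.** The point holds and must be fixed. The protocol commits to a life-table and log-rank analysis of an undefined event, while 0 of its 11 endpoint quantities is an event and the efficacy data come from two time points in patients who already have cirrhosis. As stated, the analysis estimates no effect on any primary or secondary endpoint, and the section names no method that fits the continuous markers.

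This conclusion is qualitative and needs no assumption beyond the text. The power losses and event counts are illustrations only. They rest on assumed normality, effect size, cut-points, control risks and no dropout, for one 30 against 30 comparison. The subgroup-interaction and significance-level sentences are not in question.

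**What to change.** Replace the life-table and log-rank sentence with wording such as: *The month-6 value of each fibrosis marker, and of CDR, stool bile acids and cytokines, is compared between randomised groups by ANCOVA adjusted for that marker's baseline value, on a scale (log or original) fixed for each marker before data are seen, with estimates and 95% confidence intervals.*

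Keep a life-table and log-rank analysis only as a secondary analysis, for an event with a written definition and stated assessment times. State which event the IRRs refer to, or delete that sentence.

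The cost is one paragraph of wording, with no new patients or data. The scale must be settled in advance. The gain in precision depends on the correlation r between baseline and month 6, which the protocol does not give. The detectable difference at 80% power is about 0.736 × √(1 − r²) SD:

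- r = 0: 0.736 (57 rather than 58 df, so almost nothing is lost)
- r = 0.3: 0.70
- r = 0.5: 0.64
- r = 0.8: 0.44

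For FIB-4 the entry threshold truncates the baseline range, which tends to lower r, so the gain there may be small.
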